3.1 Handling of Missing Data

- Missing data from CRFs will be proven within the data collection in OpenClinica and clarified by queries to the monitoring.
- For tracker variables datasets of two eligible weeks (10 working days) are needed. If less than two eligible weeks are available, daytimes variables of previous weeks will be used.
- No other replacement of missing data will take place.

4 Objectives

4.1 Primary Objective

According to the HEMATITIE study protocol (version V1.0, 09/20/2016) the primary objective is "to observe changes in physical activity in patients with newly initiated therapy with 3D regimen between baseline (before treatment start) and post-treatment week 12".

4.2 Secondary Objectives

The secondary objectives include the following endpoints:

- To correlate subjective fatigue (assessed by means of FSS) and physical activity (measured with an electronic activity tracker) at baseline, during and after 12 weeks of treatment with 3D regimen.
- To observe the proportion of patients achieving sustained virologic response (SVR12) after treatment with 3D regimen (defined as HCV not detectable, 12 weeks after the last dose of 3D regimen).
- To observe sleep efficiency (assessed by means of activity tracker) at baseline, during and after 12 weeks of treatment with 3D regimen.

5 Populations

5.1 Overall Population (OP)

The overall population consists of all documented patients signing the informed consent and meeting all inclusion and no exclusion criteria. Descriptive and safety parameters will be analyzed for this population.

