#### **11.1.4 Serious-, non Serious Adverse Event and Pregnancy Collection Period**

SAE, AE and pregnancy will be reported to AbbVie from the time the physician obtains the patient's authorization to use and disclose information (or the patient's informed consent) until 30 days or 5 half-lives following the intake of the last dose of physician-prescribed treatment, whichever period is longer.

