5.2 Analysis Populations (ITT and mITT)

The statistical analyses will be performed for the intention-to-treat population (ITT) and the modified ITT population (mITT) as well. The ITT consists of all documented patients of the overall population with treatment as intended to protocol and received study medication at least once. Additionally, mITT consists of all patients of the ITT which take part at all five visits. For ITT and mITT descriptive and safety parameters will be analyzed. Primary and secondary endpoints will be analyzed for mITT.

6 Statistical Methods

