6.2 Descriptive Analysis

The results of descriptive analyses will be shown in common tables for the populations OP, ITT and mITT where quantitative parameters will be shown with number (N), number of missings (miss), mean, standard deviation, minimum, maximum and quartiles (q1, q2 = median and q3). Qualitative parameters will be presented with number (N), number of missings (miss), total and relative frequency.

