6.3.3 Subgroup Analyses

According to the HEMATITE study protocol (version 1.0, 09/20/2016) „subgroup analyses will be provided for patients who achieve/do not achieve SVR12 after treatment with 3D regimen“. These analyses will be performed for ITT and mITT.

Daytime activity, FSS and sleep efficiency will be compared between following groups:

- Patients with Ribavirin vs. patients without Ribavirin at visit V2, V3, V4 and V5.
- Women vs. men at each visit.
- Patients with different fibrosis stages (F0, F1, F2 or F3) at each visit.
- Patients with different age categories (median split) at each visit.

Additionally for patients with GT1a vs. patients with GT1b FSS will be compared at each visit.

All statistical analyses will be performed by SPSS® for Windows, version 22.0.

7 Time table

The following temporary periods of time are planned:

| | |
|----------------------------------|------------------|
| Last patient out | April 2018 |
| Data input until | May 2018 |
| Cleanfile | June 2018 |
| Statistical analyses | Juli/August 2018 |
| Integrated Clinical Study Report | September 2018 |

Deviations from this plan because of unexpected occurrence are possible.

8 Planned tables for the statistical part

| Number | Items | Database/Variables |
|--|--|--|
| 1 Information to the study course | | |
| 1.1 | Enrolled/dropped out patients | Database 1 – Visit 1 (Day -28) |
| 1.2 | Study visits and study termination | Database 1 – Visit 1 (Day -28) – Visit 5 (Day 168, SVR12) |
| 1.3 | Patient eligibility criteria | Database 1 – Visit 1 (Day -28) |
| 2 Patients baseline characteristics | | |
| 2.1 | Demographics | Database 1 – Visit 1 (Day -28) |
| 2.2 | Medical history | Database 1 – Visit 1 (Day -28) |
| 2.3 | Fatigue severity scale (FSS) | Database 1 – Visit 1 (Day -28) |
| 2.4 | HCV history | Database 1 – Visit 1 (Day -28) |
| 2.5 | Vital signs | Database 1 – Visit 1 (Day -28) |
| 2.6 | Laboratory | Database 1 – Visit 1 (Day -28) |
| 2.7 | Smoking/alcohol status | Database 1 – Visit 1 (Day -28) |
| 2.8 | Activity tracker | Database 2 – Tracker data |
| 2.9 | Concomitant medication | Database 1 – Visit 1 (Day -28) |
| 3 Patients characteristics during study | | |
| 3.1 | Activity tracker | Database 2 – Tracker data |
| 3.2 | (S)AEs and concomitant medication | Database 1 – Visit 2 (Day 1) – Visit 5 (Day 168, SVR12) |
| 3.3 | Fatigue severity scale (FSS) | Database 1 – Visit 2 (Day 1) – Visit 5 (Day 168, SVR12) |

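### No planned safety population includes patients who took the 3D regimen but are later found ineligible

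*SAP*

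**What the plan says.** SAP section 5 defines three populations, each nested in the one before.

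- **OP (section 5.1):** "all documented patients signing the informed consent and meeting all inclusion and no exclusion criteria". The SAP adds: "Descriptive and safety parameters will be analyzed for this population".
- **ITT (section 5.2):** "The ITT consists of all documented patients of the overall population with treatment as intended to protocol and received study medication at least once".
- **mITT (section 5.2):** "mITT consists of all patients of the ITT which take part at all five visits".

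On safety in the two smaller sets, section 5.2 states: "For ITT and mITT descriptive and safety parameters will be analyzed". Section 6.2 names the same three sets for presentation: "The results of descriptive analyses will be shown in common tables for the populations OP, ITT and mITT". In the list of planned tables in SAP section 8, adverse events are table 3.2, which covers visits 2 to 5 and names no other population.

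Protocol section 11.1.4 sets the start of collection without reference to eligibility: "SAE, AE and pregnancy will be reported to AbbVie from the time the physician obtains the patient's authorization". Footnote 1 of the visit table in protocol section 9.1.2 also starts collection at the signing of consent.

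**The concern.** A safety summary normally answers a simple question: among the people who took the drug, what happened? Eligibility matters for whether an efficacy result applies to the target population. It does not change the fact that a patient was exposed. Here eligibility is the entry condition for every set in which safety is tabulated, so exposure alone does not bring a patient into any table.

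Such patients could plausibly occur. Several criteria in protocol section 9.2.1 rest on older information or on judgement and could be found breached after dosing:

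- genotype 1 infection may have been confirmed up to 36 months before, or be left to the physician's discretion;
- absence of cirrhosis may rest on clinical signs;
- other causes of fatigue, such as cancer or a hormonal disorder, must be absent.

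Under section 9.1.1 the FSS result may also be up to 3 months old at visit 1. Unrecognised cirrhosis or an undetected comorbidity is exactly the kind of case that a reader of the safety section would want to see.

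At stake is whether the report's adverse event tables describe all exposed patients or only those whose eligibility held up.

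**Working it through.** There is no figure in the plan to reproduce. The check is one of set membership.

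**Inputs.** OP = consented and fully eligible (SAP 5.1). ITT = OP, at least one dose, and treatment as intended under the protocol (SAP 5.2). mITT = ITT and all five visits attended (SAP 5.2). Safety is planned for OP, ITT and mITT (SAP 5.1, 5.2).

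**Inclusion chain.** mITT ⊂ ITT ⊂ OP ⊂ (consented and eligible). Anyone outside the last set is outside all of them.

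**Types of patient against the planned sets.**

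| Consented patient | OP | ITT | mITT |
|---|---|---|---|
| Eligible, dosed as intended, all five visits | yes | yes | yes |
| Eligible, dosed, stops early and misses later visits | yes | depends on how the treatment phrase is read | no |
| Eligible, never dosed | yes | no | no |
| Dosed, eligibility breach found later | no | no | no |
| Not eligible, wore the tracker, never dosed | no | no | no |

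**Row 4** is the main point. These patients were exposed and their events are collected under protocol 11.1.4, but they have no planned table.

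**Row 2** shows how the mITT differs. Under protocol 9.1.4, a patient who discontinues the regimen is withdrawn, and where the decision falls before or during a routine visit, that visit is the last. Visit 5 is on Day 168 and treatment runs for 12 weeks, to visit 4 on Day 84. Someone who stops the drug before Day 84 and is withdrawn cannot attend all five visits, so an event that leads to early stopping is absent from the mITT tables. It remains in the OP tables if the patient was eligible.

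**Row 5** concerns events before treatment and events due to the device. Protocol 11.1.1 recognises that the tracker can cause adverse events, and it is worn from visit 1, 28 days before treatment starts. These events are collected but are tabulated only for eligible patients.

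**Is any set equal to all dosed patients?** The OP includes undosed patients and omits ineligible ones. The ITT requires a dose but omits ineligible patients, and possibly also those whose treatment deviated. The mITT omits these and everyone who missed a visit. None equals the set of all patients with at least one dose.

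**A related uncertainty.** Patients with FSS below 4 at visit 2 leave the study (protocol 9.1.1 and 9.1.4), and visit 2 is Day 1, when the regimen starts. The SAP does not say whether this counts as an eligibility breach, so their place in the OP is unclear.

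**Size.** If k of n treated patients are ineligible, and an event is equally likely in each treated patient, the chance that a single-patient event is absent from every table is k/n. The documents give no k, so any percentage would only restate an assumed count. If k = 0, no treated patient's events are lost.

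**The case against.** The strongest reply is that the gap is narrow and that nothing is lost from view. Adverse events go to the sponsor within 5 business days and serious ones within 24 hours (protocol 11.1.5 and 11.1.6), with no eligibility condition. The SAP plans a flowchart of how the populations are formed (6.1) and a table of eligibility criteria (table 1.3), so excluded patients could be counted. Eligibility is checked at visit 1, 28 days before dosing, so only breaches missed then and found later matter. Safety is neither an objective nor an endpoint, and protocol 9.7 specifies no adverse event analysis. All of this is correct. It limits the importance of the point but does not supply the missing table.

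A reader might also infer more than the documents support:

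- **That all safety tables are selected by adherence.** They are not. The OP has no adherence or visit condition, so eligible patients who deviate or stop early stay in its tables.
- **That on-treatment rates are necessarily diluted by undosed patients.** The OP does include such patients, but the ITT requires at least one dose and safety is analysed there too. Eligible patients therefore already have a dosed-only denominator.
- **That the ITT definitely drops patients whose treatment deviated.** The phrase about treatment as intended is unclear. It may mean only that the 3D regimen was the planned treatment, and the protocol leaves treatment to routine practice and the label (9.1 and 9.1.3).
- **That events are concealed.** Individual reporting to the sponsor covers ineligible patients as well.
- **That safety tables on the OP and mITT should be removed.** This is a matter of preference. Extra tables do no harm once an all-treated set exists.

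**Conclusion.** The point holds as a defect of tabulation. Followed as written, the SAP leaves any treated patient with an eligibility breach out of every planned safety table, and it defines no set of all patients who took at least one dose. This follows from stated definitions, not from missing detail. It rests on two assumptions: that the OP criterion is applied as worded, and that no unlisted safety set or listing is intended.

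The effect on the results cannot be sized from the documents and may be nil. Collection, expedited reporting and the efficacy analyses are untouched. The change is still worth making before the SAP is signed, which its introduction places before database closure, because afterwards the choice of safety set would be made with knowledge of who is affected.

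**What to change.** Add to SAP section 5 a safety set of all consented patients with at least one dose of the 3D regimen, regardless of eligibility or adherence. Name it as the main set for on-treatment adverse events in planned table 3.2.

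Show pre-treatment and device-related events separately, for all consented patients who received a tracker.

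Keep the OP, ITT and mITT safety tables, if wanted, as supplementary presentations. State that the mITT tables omit patients who stopped early and missed later visits.

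The cost is a few sentences in the SAP and one more set of tables. The data are already collected, and no efficacy analysis changes. If no ineligible patient was treated, the new set still gives a clear denominator of everyone who took the drug.

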5.2 Analysis Populations (ITT and mITT)

The statistical analyses will be performed for the intention-to-treat population (ITT) and the modified ITT population (mITT) as well. The ITT consists of all documented patients of the overall population with treatment as intended to protocol and received study medication at least once. Additionally, mITT consists of all patients of the ITT which take part at all five visits. For ITT and mITT descriptive and safety parameters will be analyzed. Primary and secondary endpoints will be analyzed for mITT.

6 Statistical Methods

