**9.3 Variables**

**9.3.1 Primary Variable**

- Change of mean daytime physical activity between baseline (before treatment start) and post-treatment week 12

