6.1 Flowchart

The formation of the populations will be described by a Consort-Flowchart.

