6.3 Statistical Analysis

6.3.1 Primary Endpoint

The primary endpoint, the change of the mean daytime physical activity between baseline (before treatment start) and post-treatment week 12, will be calculated and analyzed by t-test or Wilcoxon-test, depending from the distribution of the data (normal or not). The significance level will be set to $\alpha = 0.05$, the test will be performed two-sided.

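### SAP 5.2 ties the primary and secondary endpoints to attendance at all five visits, which drops patients who missed only V3 or V4 but have evaluable primary data

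*SAP*

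**What the plan says.** SAP 5.2 defines the modified set: "mITT consists of all patients of the ITT which take part at all five visits". It closes with: "Primary and secondary endpoints will be analyzed for mITT". For ITT the same section names descriptive and safety parameters. Its opening sentence, however, says that statistical analyses are done in both ITT and mITT, and SAP 6.3.3 runs the subgroup analyses by SVR12 status in both.

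The primary endpoint in SAP 6.3.1 is "the change of the mean daytime physical activity between baseline (before treatment start) and post-treatment week 12", as in Protocol 9.3.1. On tracker data, SAP 3.1 states: "For tracker variables datasets of two eligible weeks (10 working days) are needed". Non-eligible days are filled from preceding weeks, and nothing else is imputed. SVR12 is "defined as HCV not detectable, 12 weeks after the last dose of 3D regimen" (SAP 4.2).

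Two provisions make the exclusion partly visible: "The formation of the populations will be described by a Consort-Flowchart" (SAP 6.1), and "The results of descriptive analyses will be shown in common tables for the populations OP, ITT and mITT" (SAP 6.2).

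**The concern.** The rule for entering the analysis does not match the data that the endpoint uses. V3 (Day 28) and V4 (Day 84) contribute nothing to the primary change, yet missing either one removes the patient from it. The same patient also drops out of the changes at the visits that he or she did attend.

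Two things are at stake. Usable data are discarded, which costs precision. The single-arm pre-post mean is also conditioned on attendance at visits that the endpoint does not need. Separately, because the SAP names ITT in some places and mITT in others, it does not settle which population carries the main result for each endpoint.

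**Working it through.** **1. What each endpoint needs, against what the set demands.**

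| Endpoint | Data needed | Visits demanded by mITT |
|---|---|---|
| Primary change | Baseline window (V1 to V2) and pre-V5 window, 10 eligible working days each | V1 to V5 |
| Change at one visit (SAP 6.3.2) | Baseline and that visit | V1 to V5 |
| SVR12 | Last-dose date and the viral load 12 weeks later | V1 to V5 |

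**2. Can the excluded patient exist?** Yes, on the protocol's own terms.
- The patient keeps the tracker for the whole study, and data are extracted after the last visit (Protocol 9.1.1).
- The last wear cycle is prompted by a phone call on Day 140, not by attendance at V4 (Protocol 9.1.2).
- The specific termination criteria in Protocol 9.1.4 are unsuitability for the regimen under the label, stopping treatment, too little tracker wear before a visit, and FSS below 4 at V2. A missed visit is not among them.

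**3. How wide is the group?** Narrow. The patient must stay on treatment, satisfy the wear rule before every visit, attend V1, V2 and V5, and miss V3 or V4 altogether. No visit windows are stated, so a late V3 or V4 may still count as attended.

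**4. The plan's own figure.** Protocol 9.5 gives 80% power for 100 patients, effect size 0.29, two-sided one-sample t-test, 5% level. With the noncentral t distribution (df = n − 1, noncentrality 0.29 × √n), n = 100 gives 0.29 × 10 = 2.90 and power of 81.9%. That agrees with the stated 80%. The smallest n that reaches 80% is 96 (80.3%), so the margin is four patients.

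**5. Illustration.** The documents give no missed-visit rate, so the exclusions below are assumptions. The half-width of the 95% CI for the mean change, in SD units, is t(0.975, n − 1)/√n.

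| Excluded (assumed) | n | 0.29 × √n | Power | CI half-width (SD) |
|---|---|---|---|---|
| 0 | 100 | 2.900 | 81.9% | 0.198 |
| 2 | 98 | 2.871 | 81.1% | 0.200 |
| 5 | 95 | 2.827 | 79.9% | 0.204 |
| 10 | 90 | 2.751 | 77.7% | 0.209 |

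Ten exclusions cost 81.9 − 77.7 = 4.2 points of power and widen the interval by a factor of 0.209/0.198, or about 6%. The starting figure of 100 is the enrolment target, before withdrawals for FSS below 4 at V2 and before dropout, so the real base is probably lower.

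**The case against.** **The affected group may be close to empty.** Protocol 9.1.4 already removes patients who stop treatment or wear the tracker too little, and late visits can count. This stands, and it limits the size of the point. It does not justify a rule that discards evaluable data.

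**ITT is not absent from the outcome analyses.** A reader might infer that the SAP plans no ITT estimate, interval or test at all. The text does not support that. SAP 5.2 opens with both populations, SAP 6.3.3 uses both for the SVR12 subgroups, and the descriptive tables in SAP 6.2 cover ITT and might include the change score. What can be said is that the closing sentence of SAP 5.2 assigns the endpoints to mITT, and that no section clearly puts a main primary or secondary analysis in ITT.

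**Missing V4 may leave SVR12 incomplete.** A reader might also infer that a patient who missed V4 always has complete SVR12 data. That goes too far. SVR12 is timed from the last dose, treatment compliance is scheduled only at V3 and V4 (Protocol 9.1.2), and planned table 3.4 in SAP section 8 takes regimen data from V2 to V4. The date might be recovered later, but this is not assured. The primary endpoint is unaffected.

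**A fixed cohort has merit.** The same patients at every visit make by-visit means and correlations easier to compare. That is a good reason to keep the five-visit set as a supporting analysis, but not as the only clear home of the primary endpoint.

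**The study calls itself exploratory.** Protocol 9.5 says so, and small power losses then matter less. Yet Protocol 9.5 also states a power, and Protocol 9.7 and SAP 6.3.1 plan a significance test on the primary variable.

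**Conclusion.** The point holds and is modest. As written, SAP 5.2 drops patients with evaluable primary data because they missed a visit that the primary endpoint does not use, and the SAP is inconsistent about where ITT applies.

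The size cannot be determined from the documents. With 2 to 5 assumed exclusions from 100, power stays near the stated 80% and the interval hardly changes. With 10 it falls to 77.7%. If most patients who miss V3 or V4 also lack V5, the loss from this rule is near zero.

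A reader might infer that restricting to full attenders inflates the apparent gain in activity. The documents do not support a direction: they do not say how patients who miss an intermediate visit differ from the rest.

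**What to change.** Amend SAP 5.2 and 6.3.1 before the database is closed:
- **Primary endpoint:** ITT patients with an evaluable baseline window and an evaluable pre-V5 window, 10 eligible working days each after the planned replacement, regardless of V3 or V4 attendance.
- **Change at each visit:** ITT patients with baseline and that visit.
- **SVR12:** ITT patients with a recorded last-dose date and a viral load at post-treatment week 12, reporting how many lack either.
- **Sensitivity analysis:** the five-visit mITT, which preserves a fixed cohort for comparing visits.
- **Clarity:** name one main population for each endpoint, and bring the opening and closing sentences of SAP 5.2 and the statement in SAP 6.3.3 into line with it.

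The cost is SAP wording, with no new data. The number analysed will vary by endpoint and visit and must be shown in each table. Selection on having V5 data remains, because this change removes only the part due to V3 and V4 attendance.

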### 9.1.4 Termination Criteria

A patient may withdraw from the study at any time. The investigator may discontinue any patient's participation for any reason. AbbVie AG may interrupt/stop the study at any time for any reason.

If a patient withdraws or is lost to follow-up, the reason for withdrawal will be recorded in the CRF if voluntarily shared by the patient. In case of study termination, the investigator must ensure that the patient returns the activity tracker, and that no subsequent activity tracker will be shipped to the patient.

Specifically, the following termination criteria apply:

- Patients not eligible for treatment with 3D regimen in accordance with the Swiss product label and according to the investigator's judgment will discontinue study participation.
- Patients who discontinue treatment with 3D regimen or who do not wear the activity tracker for at least 3 weeks before each visit will be withdrawn from the study. In case the decision to discontinue treatment with 3D regimen was taken before or during a routine clinic visit, this visit will be considered the last study visit. The last dose of treatment of 3D regimen will be recorded in the CRF.
- Patients with an average FSS score < 4 at visit 2 will discontinue the study.

Following discontinuation of the study, the patient will be treated in accordance with the investigator's best clinical judgment.

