6.3.2 Secondary Endpoints

For the secondary endpoints „change of FSS between baseline, during and after 12 weeks“ the difference between baseline and the respective follow-up visits will be calculated and

shown with 95% confidence intervals (95%-CI). This analysis will also be performed for the parameters daytime activity and sleep efficiency.

Furthermore for daytime activity, FSS and sleep efficiency 95%-CI will be provided at baseline, during the study and after 12 weeks.

The correlation between mean daytime physical activity and FSS will be analyzed for each visit and for the changes between baseline and follow-up visits using Spearman's rank correlation coefficient.

The proportion of patients achieving SVR12 will be calculated and shown with 95 % confidence interval.

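### The planned SVR12 rate is a five-visit completer rate, and no SVR12 proportion with a confidence interval is planned for all dosed patients

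*SAP*

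**What the plan says.** **Endpoint.** SVR12 is a secondary variable in Protocol 9.3.2 and a secondary objective in SAP 4.2. The Protocol 9.3.2 definition needs one thing only: undetectable HCV RNA 12 weeks after the last dose actually taken. SAP 6.3.2 plans: "The proportion of patients achieving SVR12 will be calculated and shown with 95 % confidence interval". It names no denominator.

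**Population.** SAP 5.2 says "Primary and secondary endpoints will be analyzed for mITT" and "mITT consists of all patients of the ITT which take part at all five visits". The ITT is made up of overall-population patients "with treatment as intended to protocol and received study medication at least once". The opening of SAP 5.2 names both ITT and mITT for the statistical analyses in general. SAP 6.3.3, which includes the split by SVR12 achieved or not, says "These analyses will be performed for ITT and mITT".

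**Who leaves before V5.** V5 (day 168) is the SVR12 visit in Protocol 9.1.2. Under Protocol 9.1.4 a patient who stops 3D is withdrawn; if that decision falls before or at a routine visit, "this visit will be considered the last study visit". The same section covers patients "who do not wear the activity tracker for at least 3 weeks before each visit will be withdrawn from the study". Participation also ends for FSS below 4 at V2 (Protocol 9.1.1 and 9.1.4) and for starting 3D before four weeks of tracker wear (Protocol 9.1.1).

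**Missing results.** After CRF queries and the tracker-day rule, SAP 3.1 says "No other replacement of missing data will take place". Protocol 9.7 gives SVR12 as an example of a qualitative variable, and SAP 6.2 reports such variables with a count of missing values for the overall population, ITT and mITT. SAP 6.1 plans a flowchart of the populations. SAP section 8 plans tables of enrolled and dropped-out patients (1.1) and of visits and termination (1.2).

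**The concern.** An SVR12 rate is normally read as the share of treated patients who were cured. Here attendance at every visit decides who is counted. Patients whose treatment failed early enough, or was tolerated badly enough, to be stopped leave both numerator and denominator. So do patients withdrawn for reasons with no evident link to virology, such as poor tracker wear. Requiring all five visits also discards usable week-12 results.

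At stake are the reported rate, its interval, and the SVR12 split in SAP 6.3.3. Protocol 7.0 cites SVR rates above 95%, and readers may set this study's figure beside that. A completer rate can sit near that level whatever happened to the patients who left.

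**Working it through.** **What can be reproduced.** The documents give no SVR12 target, interval width, loss rate or number dosed, so there is no SVR12 figure to reproduce. The only design calculation (Protocol 9.5) concerns the primary endpoint and has no bearing here.

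**Inputs (all assumed).** Dosed N = 100, taken from the approximate enrolment in the protocol; 90 and 80 are also tried, since fewer may be dosed than enrolled. Failures among attenders f = 3. Excluded from the mITT L = 5, 10 or 20. Response probability among excluded patients p.

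**Formulas.**
- Completer rate r = (N − L − f)/(N − L), with an exact (Clopper–Pearson) 95% interval.
- All-dosed rate T = (N − L − f + L·p)/N.
- Rate counting missing as non-SVR M = (N − L − f)/N.
- Error of the completer rate = r − T.

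**Results, N = 100.**

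| L | r (95% CI) | r − T, p = r | r − T, p = 0.5 | r − T, p = 0 |
|---|---|---|---|---|
| 5 | 92/95 = 96.8% (91.0–99.3) | 0 | 2.34 | 4.84 |
| 10 | 87/90 = 96.7% (90.6–99.3) | 0 | 4.67 | 9.67 |
| 20 | 77/80 = 96.3% (89.4–99.2) | 0 | 9.25 | 19.25 |

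The completer rate barely moves as losses rise, so by itself it cannot signal the problem.

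**Sensitivity.** At L = 10 and p = 0 the error is 10.69 points with 90 dosed and 11.96 with 80. With 100 dosed it is 9.78 for f = 2 and 9.44 for f = 5.

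**Does counting missing as non-SVR give the right answer?** At L = 10, M = 87/100 = 87.0% (78.8–92.9). Suppose 5 of the 10 are study-procedure withdrawals who respond like attenders:
- None of the other 5 respond: T = (87 + 5 × 0.9667)/100 = 91.83%. The completer rate is 4.83 too high and M is 4.83 too low.
- Half of the other 5 respond: T = 94.33%. The completer rate is 2.33 too high and M is 7.33 too low.

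If all 10 are such withdrawals, the completer rate is unbiased and M is 9.67 too low. With no such withdrawals, r − T = 9.67 − 10p points and T − M = 10p points, so the completer rate is the closer of the two once p exceeds about 0.48. Neither rate is a correction of the other.

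**Valid result but a missed visit.** If 4 of the 10 excluded have a valid week-12 result, the observed-result rate is 91/94 = 96.8% (91.0–99.3) when all 4 responded and 89/94 = 94.7% (88.0–98.3) when 2 did. Completers give 96.7%.

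**Subgroup split.** With 3 failures and 10 unknowns, merging them would make 10 of the 13 patients in the not-achieved group unknown.

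**The case against.** The strongest reply is that the plan is neither silent nor opaque. SAP 3.1, SAP 6.2 and Protocol 9.7 together imply that a missing SVR12 result stays missing and appears as a count. The flowchart and tables 1.1 and 1.2 let a reader see how many patients lie between ITT and mITT. Withdrawal reasons go into the CRF when the patient shares them. That all stands. A reader might infer that the plan has no way of handling missing SVR12 or hides its losses; the documents do not support that. They lack an SVR12 proportion with an interval for all dosed patients, and a tabulation of missing SVR12 results by reason.

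A reader might also infer that the plan removes virologic failures from the rate. It does not: failures who attend all five visits are counted. Nor is the gap between the completer rate and the rate counting missing as non-SVR the size of the bias. That holds only if no excluded patient responded, which is unlikely if many left over tracker wear or FSS.

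The ITT clause on treatment being as intended might be taken to exclude discontinuers. The clause is undefined and that is only a possible reading, so it needs clarifying but is not a shown error.

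The references to the ITT in the opening of SAP 5.2 and in 6.3.3 do not rescue the planned rate. The sentence specific to endpoints names the mITT alone, and 6.3.3 concerns subgroup comparisons.

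Finally, the missed-visit problem is small. Most excluded patients will have left the study and have no V5 result, and in the example the rate shifts by only 0.1 to 2.0 points.

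**Conclusion.** The point holds in a limited form. The planned SVR12 proportion and interval are a five-visit completer rate. It leaves out dosed patients who stopped 3D or were lost before V5, and it discards valid week-12 results from patients who missed an earlier visit. It is biased upward only to the extent that the excluded respond less often: 0 to 9.7 points with 10 of 100 excluded, and 4.7 if half of them respond. These sizes rest on assumed numbers dosed, excluded and failing, and on why patients left.

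SVR12 is a descriptive, untested secondary endpoint in an exploratory study. The effect is therefore confined to the reported rate, its interval and the subgroup split; the primary analysis of activity is not touched by this point. It is worth settling before the SAP is signed, which the SAP places before database closure.

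**What to change.** In SAP 5.2 and 6.3.2:

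1. Report SVR12 with a 95% confidence interval for all eligible patients with at least one 3D dose. State that the treatment-as-intended clause does not remove discontinuers from this set. Use any HCV RNA result 12 weeks after the last actual dose, whichever visits were attended.
2. Show three rates side by side, each with a 95% interval: missing counted as non-SVR, labelled a conservative lower bound and not a corrected estimate; the rate among patients with an observed result; and the five-visit completer rate.
3. Tabulate dosed patients without a result by reason. Separate 3D stopped and lost to follow-up from study-procedure withdrawals (tracker wear, FSS below 4 at V2, early 3D start). Keep no result distinct from virologic failure.
4. Reconcile SAP 5.2 with 6.3.3 on the population. In the SVR12 subgroups classify by observed result only, and show patients without a result as their own category.

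The cost is SAP wording, two further proportions and one table, with no protocol change and no new data collection. The drawback is a less favourable conservative figure, which is too low wherever patients without a result did respond (by up to 9.7 points in the example). Its label and the neighbouring rates are there to prevent misreading.
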